### **10.3.2 Permanent treatment discontinuation with investigational medicinal product**

Permanent treatment discontinuation defined as any treatment discontinuation associated with the definitive decision from the Investigator or the patient not to re-expose the patient to the IMP at any time.

### **10.3.3 List of criteria for permanent treatment discontinuation**

The patients may withdraw from treatment with the IMP if they decide to do so, at any time and irrespective of the reason, or this may be the Investigator's decision. Patients should discuss stopping study medication with the site before doing so in order that questions can be addressed, glycemic therapy adjusted, and a follow-up assessment arranged. All efforts should be made to document the reasons for treatment discontinuation and this should be documented in the e-CRF.

The following reasons can lead to permanent discontinuation:

- At the patient's own request (ie, withdrawal of consent for treatment)
- If, in the Investigator's opinion, continuation with the administration of the study treatment would be detrimental to the patient's well-being
- Inter-current condition that requires permanent discontinuation of the study treatment as long as the abnormality persists and if the casual relationship of the concerned event and the IMP is possible (according to the Investigator's best medical judgment)
- Deterioration of renal function (defined as increase in serum creatinine >50% from baseline) that is not recovered after a temporary IMP discontinuation for 2 weeks
- Patient requires renal replacement therapy (transplant or dialysis)
- Pregnancy (in female patients)
- Specific request of the Sponsor.

Any abnormal laboratory value will be rechecked immediately to confirm the result before a decision is made to permanently discontinue IMP for the concerned patient.

For patients who prematurely discontinue the IMP, the assessments planned at EOT visit ([Section 10.1.3.2](#)) will be performed at the premature EOT Visit scheduled preferably prior to treatment discontinuation or as soon as possible after the time of discontinuation (at the latest at the next scheduled on-site visit). In the case of premature IMP discontinuation, PK samples

should not be drawn at the premature EOT visit, neither at all subsequent visits. The reason for IMP discontinuation will be clearly specified. This Premature EOT assessment may occur at a regularly scheduled visit or at an unscheduled visit.

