#### 8.1.1 Dose reduction

The dose maintenance will be handled according to the renal function assessed by the creatinine measurement throughout the study. If at any visit after randomization there is a rise in creatinine level (see details in Section 10.6.2), the Investigator should ensure that no reasonable explanation exists for creatinine increase. Sites will be notified by central laboratory alert if a patient has a >50% increase from Baseline level or >50% above the mean of creatinine values from the last 2 visits, where Baseline level is defined as the mean of creatinine values obtained at Screening and Randomization. The IMP should be stopped for 2 weeks. If at creatinine recheck the patient

has returned to the below threshold then IMP will be restarted at a reduced dose (ie, dose reduced via IRT to 200 mg for patients randomized to 400 mg, maintained to 200 mg for patients randomized to 200 mg, and to placebo for those randomized to placebo). Since IMP received is blinded, patients must return to the site and IRT will be contacted for this IMP re-initiation. Dose reduction can only be obtained at on-site visit by IRT. If the creatinine does not return to below the threshold, the IMP will be permanently discontinued but the patient will be asked to continue attending all study visits.

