### **10.3.1 Temporary treatment discontinuation with investigational medicinal product**

Temporary treatment discontinuation may be considered by the Investigator because of suspected AEs.

Lower extremity complications (such as skin ulcers, infection, osteomyelitis, and gangrene) requiring treatment should lead to temporary discontinuation of IMP.

If at any visit after randomization up to Week 8 there is a rise in creatinine level (ie, >50% increase from baseline level, where baseline level is defined as the mean of creatinine values obtained at Screening and Randomization) or if at any visit after Week 8 there is a rise of >50% above the mean of creatinine values from last 2 visits, the Investigator should ensure that no reasonable explanation exists for creatinine increase.

The IMP should be stopped for 2 weeks.

Re-initiation of treatment with the IMP will be done under close and appropriate clinical/and or laboratory monitoring once the Investigator has considered according to his/her best medical judgment that the responsibility of the IMP in the occurrence of the concerned event was unlikely to be related to the IMP and that the selection criteria for the study are still met (refer to [Section 7.1](#) and [Section 7.2](#)).

If at creatinine recheck the patient has returned to the below threshold then IMP will be restarted at a reduced dose (ie, dose reduced via IRT to 200 mg for those randomized to 400 mg; maintained at 200 mg for those randomized to 200 mg). Since the IMP received is blinded, patients must return to the site and IRT will be contacted for IMP re-initiation.

It is in the interest of the patient to monitor blood glucose during the temporary discontinuation period, therefore regular determination of SMBG is to be performed and documented (see [Section 9.2.1.7](#)).

For all temporary treatment discontinuations, duration should be recorded by the Investigator in the appropriate pages of the e-CRF when considered as confirmed.

Temporary treatment discontinuation decided by the Investigator corresponds to more than 1 dose not administered to the patient.

Use of any other anti-hyperglycemic medication during the time of temporary treatment discontinuation (ie, insulin during a hospitalization) is recorded as concomitant medication with the name and doses recorded in the e-CRF.

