## **10.6.2 Deterioration of renal function**

Patients will be monitored throughout the double-blind Treatment Period for signs of deterioration in renal function (eg, decrease in eGFR or increase in creatinine as defined below) as well as other routine clinical and laboratory findings (see Study Flowchart, [Section 1.2](#)). If at any visit after randomization up to Week 8 there is a rise in creatinine level (ie,  $> 50\%$  increase from baseline level, where baseline level is defined as the mean of creatinine values obtained at Screening and Randomization) or if at any visit after Week 8 there is a rise of  $> 50\%$  above the mean of creatinine values from last 2 visits, the Investigator should ensure that no reasonable explanation exists for creatinine increase and in particular the following causes:

- Medications that increase creatinine
- Decrease in cardiac output
- Obstructive uropathy
- Urinary tract infection
- Volume depletion

If addressing these causes does not reduce the creatinine level below the above stated threshold, the IMP will be stopped for 2 weeks. The dose will be handling according to the renal function assessed by the creatinine measurement throughout the study and as detailed in [Section 10.3.1](#).

If the creatinine dose not return to below the threshold, then the IMP will be permanently discontinued but the patient will be asked to continue attending all study visits.

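### After Week 8, Protocol 10.3.3 measures the >50% creatinine rise from baseline while the stop-and-restart sections use the last-two-visit mean, so one recheck can qualify for restart and still fit the 10.3.3 definition

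*Protocol*

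**What the plan says.** **Stop-and-restart pathway.** Protocol 10.3.1 uses baseline (the mean of the Screening and Randomization values) up to Week 8 and then changes the reference: "if at any visit after Week 8 there is a rise of >50% above the mean of creatinine values from last 2 visits". Section 10.6.2 sets the same trigger. The synopsis refers to the previous two visits, and flow-chart footnote s (Protocol 1.2, repeated in SAP Appendix E) to the arithmetic mean of the last two. If the rise persists, study drug is withheld for two weeks and creatinine is rechecked. Both outcomes turn on the threshold. For restart, 10.3.1 says: "If at creatinine recheck the patient has returned to the below threshold then IMP will be restarted at a reduced dose". The synopsis and 8.1.1 agree. If creatinine does not fall below the threshold, 10.6.2 says "then the IMP will be permanently discontinued", again matched in the synopsis and 8.1.1. Section 10.3.1 alone adds that the investigator must consider a link to study drug unlikely and "that the selection criteria for the study are still met".

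**Permanent-discontinuation list.** Section 10.3.3 is introduced by "The following reasons can lead to permanent discontinuation" and includes "Deterioration of renal function (defined as increase in serum creatinine >50% from baseline) that is not recovered after a temporary IMP discontinuation for 2 weeks". It mentions neither Week 8 nor the two-visit mean, and gives no reference for recovery.

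**Laboratory alert.** Section 8.1.1 sends the reader to 10.6.2 for details of the rise. It then says that the site is alerted when a patient has a ">50% increase from Baseline level or >50% above the mean of creatinine values from the last 2 visits", with no Week 8 split.

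**The concern.** Section 10.3.3 is where an investigator looks for the grounds for a permanent stop, and it states a different reference from the pathway that leads there. In CKD stage 4 patients, one creatinine value after Week 8 can therefore be classified in two ways: below the threshold, so drug is restarted at a reduced dose, or still within the stated definition of renal deterioration. Two investigators could act differently on the same value, each citing the protocol.

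The alert comes from the central laboratory and the dose reduction goes through IRT. Those specifications are not in the documents, and the protocol text does not settle which reference they should carry. On the analysis side, SAP 2.4.3.1 counts dose interruptions and reductions from an e-CRF question asking whether the interruption was for a creatinine increase as laid down in the protocol. That answer depends on which section is taken as the rule.

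**Working it through.** The plan gives no figure to reproduce here, so the check is threshold arithmetic. The creatinine values below are assumed, for illustration only.

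**Inputs.** B = baseline creatinine. M = mean of the last two visits. C = recheck value. From 10.3.3, the definition is met when C > 1.5B. From the synopsis, footnote s, 10.3.1 and 10.6.2, the threshold after Week 8 is 1.5M. The eGFR formula (SAP 2.5.1, MDRD, non-Black man) is 175 × creatinine^-1.154 × age^-0.203. Entry requires eGFR of 15 to <30 (Protocol 7.1), and exclusion E 19 rules out eGFR below 15.

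**Step 1: when both apply.** C is below the restart threshold and still meets the 10.3.3 definition when 1.5B < C < 1.5M. This is possible whenever M > B. As multiples of baseline, the range is 1.50 to 1.65 for M/B = 1.1, 1.50 to 1.80 for 1.2, and 1.50 to 1.95 for 1.3.

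**Step 2: example, age 60.** B = 2.5 mg/dL (eGFR 26.5) and M = 2.75. The threshold is 1.5 × 2.75 = 4.125. A value of 4.2 (eGFR 14.6) triggers the pathway. A recheck of 4.0 (eGFR 15.4) is below 4.125, but 4.0/2.5 = 1.60 × baseline.

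**Step 3: the restart condition in 10.3.1.** If eGFR must be at least 15 at restart, the overlap needs a baseline eGFR above 15 × 1.5^1.154 = 23.9. With baseline eGFR g, the highest admissible recheck is (g/15)^(1/1.154) × baseline. Dividing that multiple by 1.5 gives the M/B that opens the whole range.

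| Baseline eGFR | Highest recheck, × baseline | M/B that opens the full range |
|---|---|---|
| 24 | 1.503 | 1.002 |
| 25 | 1.557 | 1.038 |
| 26 | 1.611 | 1.074 |
| 28 | 1.717 | 1.145 |
| 29.9 | 1.818 | 1.212 |

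Below about 24 there is no overlap under this condition.

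**Step 4: the reverse case.** B = 2.4 and M = 2.1, so the threshold is 1.5 × 2.1 = 3.15. A value of 3.5 triggers. A recheck of 3.3 is 57% above M, so 10.6.2 requires a permanent stop. It is only 38% above B (3.3/2.4 = 1.375), so the 10.3.3 definition is not met.

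**Step 5: which two visits at the recheck.** The text does not say whether the threshold stays fixed at the trigger. Take B = 2.4, last two visits 2.8 and 3.0 (M = 2.9), and a trigger of 4.5. The fixed threshold is 1.5 × 2.9 = 4.35. If the trigger visit enters the mean, it becomes 1.5 × (3.0 + 4.5)/2 = 5.625. A recheck of 3.8 is below both, and is 58% above baseline.

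**The case against.** **A reader might infer that 10.3.3 orders a permanent stop where 10.3.1 orders a restart.** The documents do not support that. The 10.3.3 list only names reasons that may lead to discontinuation, and its renal item has a second limb: no recovery after the two-week stop. That stop comes from the pathway in 10.3.1 and 10.6.2, so recovery can reasonably be read as falling below the pathway threshold. On that reading, a patient who qualifies for restart has recovered and the full criterion is not met. In the reverse case, 10.3.3 does not forbid the stop that 10.6.2 requires. What stands is that 10.3.3 never says this. Its only stated reference is baseline, so reading recovery against baseline is equally open.

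**A reader might infer that 8.1.1 sets a second rule for the period after Week 8.** Its pointer to 10.6.2 may simply import the split. If the sentence is taken literally, it also names the two-visit mean before Week 8, so one cannot say that all sections agree up to that visit. Either way this is loose wording and secondary to 10.3.3.

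**The selection-criteria clause might be thought to remove the overlap.** It narrows it, as Step 3 shows. The synopsis and 8.1.1 restart rules do not state that clause.

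**Conclusion.** The inconsistency is real and should be corrected. After Week 8, 10.3.3 and the pathway sections state different references for the same >50% rule, and 10.3.3 leaves recovery undefined. It is a mismatch of definition and of force (permissive in 10.3.3, mandatory in 10.6.2).

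It concerns creatinine checks after Week 8: the scheduled visits at Weeks 12, 18, 26, 39 and 52, and the two-weekly recheck visits in flow-chart footnote e. The overlap requires a two-visit mean above baseline and, if eGFR of at least 15 is required at restart, a baseline eGFR of about 24 to <30. The documents give no basis for how often this would occur.

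A reader might infer that the primary result is at risk. The documents do not support that: patients are analysed as randomized, and HbA1c measured after stopping study drug is used (SAP 2.4.4). Stopping early matters there mainly through the choice of imputation model when the Week 26 value is missing (SAP 2.4.4.1). The SAP count of creatinine-related interruptions may be affected. A stop on a baseline-only alert after Week 8 follows 8.1.1 read literally, but not 10.3.1 or 10.6.2.

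**What to change.** Reconcile Protocol 10.3.3 with the synopsis, footnote s, 10.3.1 and 10.6.2: state whether the Week 8 split applies there and what recovery is measured against. Bring the alert sentence in 8.1.1 into line with the same text. State whether the threshold applied at the recheck is the one crossed at the trigger. Then check that the central laboratory alert, the IRT programming and the e-CRF question behind the SAP interruption count follow the agreed wording. Which reference applies is a clinical decision for the sponsor.

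The cost is a wording amendment centred on two protocol sections, with the recheck clarification, plus a check of the alert, IRT and one e-CRF question. No new procedures or visits are needed.

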#### **10.3.4 Handling of patients after permanent treatment discontinuation**

Every effort should be made to maintain patients in the study. Patients should be followed up according to the study procedures as specified in this protocol up to the scheduled date of study completion, or up to recovery or stabilization of any AE to be followed up as specified in this protocol, whichever comes later.

If a patient prematurely discontinues study treatment, a premature EOT visit (see [Section 10.1.3.2](#)) should be scheduled prior to treatment discontinuation, if possible. If not possible, the Premature EOT should be scheduled as soon as possible after treatment discontinuation. In the case of early discontinuation, no sample for measuring plasma concentration should be taken at the premature EOT visit, or at any subsequent visit. For patients who discontinue treatment but remain in the study, the remaining study visits should occur as scheduled where possible. The IRT should be notified of EOT.

All cases of permanent treatment discontinuation should be recorded by the Investigator in the appropriate pages of the e-CRF.

#### **10.3.5 Procedure and consequence for patient withdrawal from study**

Patients may withdraw from the study before study completion if they decide to do so, at any time and irrespective of the reason. Withdrawal of consent for treatment should be distinguished from withdrawal of consent for follow-up visits. Patients will be told that they are free to withdraw from the study at any time without any adverse effect on their care. However, if they no longer wish to take the IMP, they will be encouraged to remain in the study and attend the remaining study visits. The value of all their study data collected during their continued involvement will be emphasized as important to the public health value of the study.

If possible, the patients are assessed using the procedure normally planned for the end of study visit.

Patients who withdraw should be explicitly asked about the contribution of possible AEs to their decision to withdraw consent, and any AE information elicited should be documented. Preferably the patient should withdraw consent in writing and, if the patient or the patient's representative refuses or is physically unavailable, the site should document and sign the reason for the patient's failure to withdraw consent in writing.

All confirmed study withdrawals should be recorded by the Investigator in the appropriate screens of the e-CRF and in the patient's medical records. In the medical record, at least the date of the withdrawal and the reason should be documented.

For patients who fail to return to the site, unless the patient withdraws consent for follow-up, the Investigator should make the best effort to re-contact the patient (eg, contact patient's family or

private physician, review available registries or health care databases), and to determine his/her health status, including at least his/her vital status. Attempts (3 phone call attempts followed by a certified letter) to contact such patients must be documented in the patient's records (eg, times and dates of attempted telephone contact, receipt for sending a registered letter).

Patients who have withdrawn from the study cannot be re-randomized (treated) in the study. Their inclusion and treatment numbers must not be reused.

## **10.4 OBLIGATION OF THE INVESTIGATOR REGARDING SAFETY REPORTING**

### **10.4.1 Definitions of adverse events**

#### **10.4.1.1 Adverse event**

An AE is any untoward medical occurrence in a patient or clinical investigation patient administered a pharmaceutical product and which does not necessarily have to have a causal relationship with the IMP.

#### **10.4.1.2 Serious adverse event**

An **SAE** is any untoward medical occurrence that at any dose:

- Results in death, or
- Is life-threatening, or

**Note:** The term "life-threatening" in the definition of "serious" refers to an event in which the patient was at risk of death at the time of the event; it does not refer to an event which hypothetically might have caused death if it were more severe

- Requires inpatient hospitalization or prolongation of existing hospitalization, or
- Results in persistent or significant disability/incapacity, or
- Is a congenital anomaly/birth defect, or
- Is a medically important event

Medical and scientific judgment should be exercised in deciding whether expedited reporting is appropriate in other situations, such as important medical events that may not be immediately life-threatening or result in death or hospitalization but may jeopardize the patient or may require medical or surgical intervention (ie, specific measures or corrective treatment) to prevent one of the other outcomes listed in the definition above.

**Note:** The following list of medically important events is intended to serve as a guideline for determining which condition has to be considered a medically important event. The list is not intended to be exhaustive:

- Intensive treatment in an emergency room or at home for:
  - Allergic bronchospasm
  - Blood dyscrasias (ie, agranulocytosis, aplastic anemia, bone marrow aplasia, myelodysplasia, pancytopenia, etc)
  - Convulsions (seizures, epilepsy, epileptic fit, absence, etc)
- Development of drug dependence or drug abuse
- ALT >3 times ULN + total bilirubin >2 times ULN or asymptomatic ALT increase >10 times ULN
- Suicide attempt or any event suggestive of suicidality
- Syncope, loss of consciousness (except if documented as a consequence of blood sampling)
- Bullous cutaneous eruptions
- Cancers diagnosed during the study or aggravated during the study
- Chronic neurodegenerative diseases (newly diagnosed) or aggravated during the study.

#### **10.4.1.3 Adverse event of special interest**

An AESI is an AE (serious or nonserious) of scientific and medical concern specific to the Sponsor's product or program, for which ongoing monitoring and immediate notification by the Investigator to the Sponsor is required. Such events may require further investigation in order to characterize and understand them. Adverse events of special interest may be added, modified or removed during a study by protocol amendment.

- Pregnancy of a female patient entered in a study as well as pregnancy occurring in a female partner of a male patient entered in a study with IMP/NIMP:
  - Pregnancy occurring in a female patient included in the clinical trial or in a female partner of a male patient entered in the clinical trial. It will be qualified as an SAE only if it fulfills one of the seriousness criteria (see [Section 10.4.1.2](#))
  - In the event of pregnancy in a female patient, IMP should be discontinued
  - Follow-up of the pregnancy in a female patient or in a female partner of a male patient is mandatory until the outcome has been determined (see [Appendix A](#))
- Symptomatic overdose (serious or nonserious) with IMP/NIMP
  - A symptomatic overdose (accidental or intentional) with the IMP/NIMP is an event suspected by the Investigator or spontaneously notified by the patient and resulting in clinical symptoms and/or signs accompanied by administration of more than twice the intended daily dose within a 24-hour period. It will be recorded in the e-CRF as an AESI with immediate notification "Symptomatic OVERDOSE (accidental or intentional)" in all cases and will be qualified as an SAE only if it fulfills the SAE

criteria. (Please note that an asymptomatic overdose with the IMP/NIMP, accidental or intentional, defined as administration of more than twice the intended daily dose within a 24-hour period, without clinical symptoms and/or signs, either suspected by the Investigator or spontaneously notified by the patient, not based on accountability assessment. It will be recorded as an AE “Asymptomatic OVERDOSE, accidental or intentional”).

- ALT increase >3 times ULN

